**Drug A Protocol Summary**  
**Protocol No. NDP- 1 003**

- 1. Project Status:** Phase III
- 2. Purpose:** To evaluate the safety and efficacy of Drug A versus cefuroxime in the treatment of community acquired pneumonia
- 3. Design:** Multicenter, prospective, randomized Phase III study
- 4. Number of Subjects:** Approximately 450 outpatient subjects to yield 400 subjects that met the criteria, minimum of 200 subjects in each of two treatment groups. 20 subjects will be enrolled from each site
- 5. Types of Subjects:** Male and female subjects with clinical symptoms of community-acquired pneumonia who are appropriate candidates for oral therapy
- 6. Key Inclusion Criteria:** Subject must be at least 18 years old with clinical signs and symptoms of acute pneumonia
- 7. Key Exclusion Criteria:** Subjects infected with a known resistant organism; acute allergic reaction to any non-antimicrobial, or a severe reaction to penicillin or any cephalosporin; renal failure; neutropenia; pregnant or nursing mothers; prior use of an investigational agent within 30 days; or previous treatment under this protocol
- 8. Comparative Agent:** Cefuroxime axetil
- 9. Dosage & Duration:** Drug A - 500 mg PO q12h x 7-14 days Cefuroxime axetil - 500 mg PO q12h for 7-14 days
- 10. Safety Parameters:** Safety evaluations will be based on changes in the physical exam and laboratory tests from pre- to post-therapy and reporting of any adverse events.
- 11. Efficacy Parameters:**
  - a. Microbiological response (2-4 days post-therapy) will be based on eradication of the pathogens isolated at admission.
  - b. Clinical response (2-4 days post-therapy) will be based on resolution of signs/symptoms and changes in radiological findings reported at admission.
- 12. Location:** Multicenter; 20-25 sites are expected to participate
- 13. Data Analysis:**

- a. Safety - adverse events and changes in physical examinations and clinical laboratory tests from pre- to post-treatment will be summarized
- b. Efficacy- the microbiological eradication rates and clinical response rates will be compared for Drug A and Cefuroxime axetil

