## **1. BACKGROUND AND RATIONALE**

Drug, A is an investigational compound in the quinolone class of antibiotics. It- has been used in Europe for 5 years for treating patients with community-acquired bacterial pneumonia, with success rates around 90%.

Although Drug A is more active in vitro than other members of its class, toxicity profiles in animal studies are similar. Accordingly, Drug A is expected to offer an opportunity to enhance the efficacy profile of quinolones without an incremental increase in adverse events.

It is anticipated that Drug A could be used once daily for many infections including mild to moderate skin, lower respiratory, and pelvic infections, as well as UTIS. Severe or life-threatening infections could be treated with a twice-daily dosing schedule.

To date, approximately 150 subjects have received Drug A in Phase I and Phase II trials in the United States. Adverse reactions were judged probably or possibly drug-related in 14.8% of courses; drug treatment had to be stopped prematurely in 3.5%. The most frequent reactions were gastrointestinal complaints (chiefly nausea, diarrhea, and vomiting), metabolic disorders (elevated SGOT, SGPT, serum creatinine or blood urea nitrogen), nervous system effects (dizziness, restlessness, tremor, and headache), and rash.

In animal toxicologic trials, Drug A and other quinolones appear to have similar safety profiles. The absorption, distribution, metabolism, and excretion appear to be similar as well, both in animals and in humans. Based on these studies, it is anticipated that the fate of administered Drug A will be comparable to that of other long acting quinolones both with respect to human safety and tolerance.

Over 40 million people have been treated with various quinolones. They have generally been well tolerated. The events considered likely to be drug-related in clinical trials in subjects receiving multiple doses were nausea, headache, dizziness, and diarrhea.

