### C. Exclusion Criteria

1. Subjects infected with a resistant organism known prior to starting therapy
2. Previous allergic or serious adverse reaction to any members of the quinolone class of antimicrobials, or a severe reaction to penicillin or any cephalosporin
3. Severe renal failure (creatinine clearance < 20 ml/min)
4. Presence of neutropenia (< 500 WBC's/mm^3)
5. Pregnant women or nursing mothers
6. Use of an investigational agent within 30 days prior to entry into the study
7. Previous treatment under this protocol

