### **A. Visit #1 - Baseline Visit**

At the baseline visit, the following will be performed:

1. Sign informed consent form
2. Pertinent medical history
3. Pertinent physical examination, including vital signs
4. Chest x-ray (PA & lateral)
5. Respiratory secretions must be obtained within the 48 hours prior to study entry for routine culture and Gram stain. Deep expectorated or auctioned sputum, transtracheal aspirates, bronchial brushings, washings, biopsies, or pleural fluid are

all acceptable. Specimens should also be cultured for *M pneumoniae*, *L. pneumophila*, and *C pneumoniae* when indicated and if the microbiology laboratory has the capability to perform these cultures.

Disk and MIC susceptibilities for all study drugs are to be performed on all aerobic pathogens isolated (except *M pneumoniae*, *L. pneumophila*, and *C pneumoniae*). Genus and species identification is required on all pathogens isolated.

6. Obtain venous blood samples and process blood at local institution:
  - a. Hematology:
    - hemoglobin
    - hematocrit
    - RBC
    - platelet count
    - WBC, including differential
  - b. Serum chemistry:

-glucose	-total bilirubin
-creatinine	-inorganic phosphorous
-BUN	-alkaline phosphatase
-total protein	-calcium
-albumin	-uric acid
-sodium	-chloride
-potassium	-CO 2
-SGOT	-LDH
-SGPT	
  - c. Pharmacokinetics (these will be shipped and analyzed at a central laboratory, see Appendix II for instructions)
7. Urinalysis, including pH, specific gravity, and microscopic examination of sediment for RBC, VIBC, and non-amorphous crystals
8. Urine pregnancy test
9. Evaluate subject for signs and symptoms of pneumonia
10. Complete confidential follow-up form
11. Assign subject number
12. Pharmacist to open randomization envelope and dispense/prescribe appropriate drug

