**E. Early Withdrawal from the Study**

In the event a subject withdraws from therapy prematurely, the same procedures as in Visit #3 (Study Days 2-4 After Completion of Therapy) should be performed at the time of study withdrawal. The reason for early therapy withdrawal should be documented on the appropriate case record form. Schedule follow-up visit, if appropriate.

To date approximately 150 subjects have been given Drug A. The most frequently reported side effects are outlined in the table below:

Possible Risk/Side Effect	How often has it	How serious is it?
---------------------------	------------------	--------------------

	occurred	
Nausea	It is expected to occur	Can be easily treated
Diarrhea	It is expected to occur	Can be easily treated
Vomiting	It is uncommon	Can be treated
Changes in certain levels in your blood chemistry	It is uncommon	Very Serious
Dizziness	It occasionally occurs	Can be treated
Restlessness	It occasionally occurs	Can be treated
Tremors	It occasionally occurs	Can be treated
Headache	It is expected to occur	Can be easily treated
Rash	It occasionally occurs	Can be treated

**Allergic reaction to any antibiotic in the past should be documented or noted by the investigator or the study coordinator because the study subject may have an allergic reaction to antibiotics used in this study. These allergic reactions may be life threatening.**

The risks of drawing blood from a vein includes discomfort at the site of the needle stick, possible bruising and swelling around the site of the needle stick, rarely an infection, and uncommonly feeling faint from the procedure.”

The risks of Drug A and Cefuroxime axetil to an unborn child are unknown. Therefore, if the study subject is capable of giving birth to or fathering a child, he/she should use adequate birth control measures while on the study. These measures may include abstinence, oral contraceptives (birth control pills), IUD, diaphragm, Norplant, approved hormone injections, condoms, or documentation of medical sterilization.

This research study involves exposure to radiation from chest x-rays. The amount of radiation exposure from this procedure(s) is equivalent to a uniform whole body exposure of 10 millirems. This is equivalent to 5 % of the amount of natural environmental radiation the average person receives annually. The risk from radiation exposure of this magnitude is too small to be detected in this population.

Severe and Unanticipated Adverse Events:

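### Two exclusion criteria contradict themselves: neutropenia is defined by a total white cell count, and the Summary's allergy exclusion does not match the full criterion on quinolones

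*Protocol*

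**What the plan says.** **Allergy.** The Protocol Summary, item 7 (Key Exclusion Criteria), lists "acute allergic reaction to any non-antimicrobial, or a severe reaction to penicillin or any cephalosporin". Section 2.2 C (Exclusion Criteria), item 2, lists "Previous allergic or serious adverse reaction to any members of the quinolone class of antimicrobials", followed by the same penicillin and cephalosporin limb as the Summary. Section 1 (Background and Rationale) gives the class of the test drug: "Drug, A is an investigational compound in the quinolone class of antibiotics". The risk text under Section V E (Early Withdrawal from the Study) asks site staff to record any past antibiotic allergy and adds: "These allergic reactions may be life threatening".

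**Neutropenia.** Summary item 7 names the condition without a count: "renal failure; neutropenia; pregnant or nursing mothers". Section 2.2 C, item 4, gives the count: "Presence of neutropenia (< 500 WBC's/mm"³. The baseline haematology panel in Section V A (Visit #1), item 6a, includes "WBC, including differential".

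**Enrolment rule.** Section 2.2 D and the Description of Study both allow entry only to subjects who fulfil every inclusion criterion and have no exclusion criterion.

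**The concern.** An eligibility criterion has to give the same answer whoever applies it, and 20 to 25 sites are expected to apply these. Each of the two statements can give different answers for the same subject.

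In item 4 of Section 2.2 C, the name refers to one cell type and the number to a wider group of cells. One investigator may apply the named condition and another the printed count. This is the operative criterion, and nothing else in the protocol settles which reading is meant.

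On allergy, the limb that differs between Summary and full list is the one that concerns the class of the test drug. Read literally, the Summary omits an exclusion that the full list requires and adds one (reactions to non-antimicrobials) that the full list does not contain. The protocol does not say which text prevails.

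At stake are the safety of the subjects concerned, who would be few in number, and avoidable eligibility deviations.

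**Working it through.** **1. Allergy: the two texts side by side.**

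| Element | Summary, item 7 | Section 2.2 C, item 2 |
|---|---|---|
| Nature of reaction | acute allergic | previous allergic, or serious adverse |
| Agent | any non-antimicrobial | any quinolone |
| Penicillin or cephalosporin, severe reaction | yes | yes |

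The third row agrees; the first two do not. Applied literally to two kinds of subject:

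- Past quinolone allergy only: not excluded by the Summary, excluded by Section 2.2 C.
- Acute allergic reaction to a non-antimicrobial only: excluded by the Summary, not excluded by Section 2.2 C.

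The conflict therefore runs in both directions, and shortening alone does not explain it. Under the enrolment rule in Section 2.2 D, a site that works through the full list still turns away the first subject.

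**2. Neutropenia: label against count.**

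Inputs: the limit of 500 per mm³ on white cells (Section 2.2 C, item 4). The white cell counts and neutrophil percentages below are assumed for illustration; the protocol gives none.

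Formula: neutrophils = total white cells × neutrophil fraction.

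Because the fraction cannot exceed 1, a total below 500 always means neutrophils below 500. The converse fails. For a total W of 500 or more, neutrophils are below 500 whenever the fraction is below 500 / W.

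| Assumed total WBC/mm³ | Assumed neutrophil fraction | Neutrophils/mm³ | Excluded by the count as written? | Fraction below which neutrophils are under 500 |
|---|---|---|---|---|
| 1,000 | 20% | 1,000 × 0.20 = 200 | No | 500 / 1,000 = 50% |
| 1,500 | 20% | 1,500 × 0.20 = 300 | No | 500 / 1,500 = 33.3% |
| 2,000 | 10% | 2,000 × 0.10 = 200 | No | 500 / 2,000 = 25% |
| 4,000 | 10% | 4,000 × 0.10 = 400 | No | 500 / 4,000 = 12.5% |

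All four have neutrophils below 500/mm³, and none meets the printed count. Taken literally, the criterion catches only a subset of those whose neutrophils fall below the same number. The baseline differential would allow either quantity to be computed, so resolving the conflict needs no new test.

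**3. What cannot be computed.** The protocol gives no frequency of quinolone allergy or of low neutrophil counts in the target population, so no expected number of affected subjects can be derived.

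**The case against.** The strongest reply concerns allergy. The Summary lists only key criteria. It omits the x-ray infiltrate, the two-symptom requirement and the creatinine clearance cut-off, so no site could settle eligibility from it alone. The full list names quinolones, and the note in Section V E would bring a past antibiotic allergy to the site's attention. The Summary wording looks like an editorial slip, and a text-reading error cannot be ruled out. Most of this stands: it limits the allergy point to a Summary that contradicts the criteria. It does not remove the point. Even if the prefix in non-antimicrobial were a reading error, any antimicrobial would still not be the quinolone class, and the description of the reaction would still differ.

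On neutropenia, it can be said that the named condition governs and the parenthesis is loose. That is a possible reading, but the parenthesis is the only quantitative definition in the protocol, and the named condition alone sets no limit. The objection that the worked cases are assumed is also fair: they show that the gap exists, not how often it occurs.

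Three stronger readings are tempting, and the protocol does not support them:

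- *That quinolone-allergic subjects can be enrolled under this protocol.* Section 2.2 C, item 2, bars them. The risk requires a site to rely on the Summary.
- *That the errors would produce exclusions after randomization falling mainly on one arm.* Allergy history is a baseline factor that randomization is expected to balance, and no section describes removing ineligible subjects by arm.
- *That a 50% chance of receiving Drug A measures the harm.* That figure is only the equal allocation. It says nothing about how many such subjects would enter.

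**Conclusion.** Both contradictions are in the text, and both should be corrected. The neutropenia criterion is the weightier, because the conflict sits in the operative list and no other section resolves it; read literally, it admits some subjects with neutrophils below the number it states. The allergy conflict is real but contained, because the full criteria already carry the quinolone exclusion.

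The size cannot be stated as a number of subjects. The conclusion on neutropenia rests on the literal reading of item 4 and on neutrophils being a subset of white cells; the worked cases use assumed differentials. The conclusion on allergy rests on the wording of the two passages and on the protocol giving neither precedence. No effect on sample size, power or alpha is claimed.

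**What to change.** - Reconcile item 7 of the Protocol Summary with item 2 of Section 2.2 C, so that both state the same allergy exclusion.
- Reconcile the label and the count in item 4 of Section 2.2 C, so that both refer to the same cell type. The measure and the threshold are clinical decisions for the sponsor and the medical monitor, and none is proposed here.

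The cost is two lines of wording and possibly a few more screen failures. The baseline blood count already includes a differential, so no procedure is added.

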## **1. BACKGROUND AND RATIONALE**

Drug, A is an investigational compound in the quinolone class of antibiotics. It- has been used in Europe for 5 years for treating patients with community-acquired bacterial pneumonia, with success rates around 90%.

Although Drug A is more active in vitro than other members of its class, toxicity profiles in animal studies are similar. Accordingly, Drug A is expected to offer an opportunity to enhance the efficacy profile of quinolones without an incremental increase in adverse events.

It is anticipated that Drug A could be used once daily for many infections including mild to moderate skin, lower respiratory, and pelvic infections, as well as UTIS. Severe or life-threatening infections could be treated with a twice-daily dosing schedule.

To date, approximately 150 subjects have received Drug A in Phase I and Phase II trials in the United States. Adverse reactions were judged probably or possibly drug-related in 14.8% of courses; drug treatment had to be stopped prematurely in 3.5%. The most frequent reactions were gastrointestinal complaints (chiefly nausea, diarrhea, and vomiting), metabolic disorders (elevated SGOT, SGPT, serum creatinine or blood urea nitrogen), nervous system effects (dizziness, restlessness, tremor, and headache), and rash.

In animal toxicologic trials, Drug A and other quinolones appear to have similar safety profiles. The absorption, distribution, metabolism, and excretion appear to be similar as well, both in animals and in humans. Based on these studies, it is anticipated that the fate of administered Drug A will be comparable to that of other long acting quinolones both with respect to human safety and tolerance.

Over 40 million people have been treated with various quinolones. They have generally been well tolerated. The events considered likely to be drug-related in clinical trials in subjects receiving multiple doses were nausea, headache, dizziness, and diarrhea.

## **2. Study Design**

### **2.1 OBJECTIVE**

The objective of this study is to evaluate the safety and efficacy of Drug A compared to orally administered cefuroxime axetil in the treatment of community-acquired pneumonia due to susceptible organisms in adults.

## **DESCRIPTION OF STUDY**

This is a multicenter, prospective, randomized, Phase III study to evaluate the safety and efficacy of Drug A compared with cefuroxime axetil in the treatment of community-acquired pneumonia in adults.

Investigators will collectively enroll approximately 450 outpatient subjects with community-acquired pneumonia to ensure clinically evaluable data from 400 subjects. The study will be terminated when 200 clinically evaluable subjects per treatment group have been prospectively enrolled. The study may be amended if necessary to ensure enrollment of sufficient numbers of subjects with infections due to critical pathogens. The data will be pooled across investigators for safety and efficacy analyses. A subject is eligible for study entry if the infection was acquired in a community setting.

Subjects who meet all the inclusion criteria and exhibit none of the exclusion criteria may be enrolled. A Potential Subject Roster, which will document the initials of each patient considered for study entry, the date of assessment, severity of diagnosis and the reasons for not enrolling any potential study subject, will be maintained at each site. As subjects qualify for the study, subject numbers will be assigned in strict sequential order at each site. Subjects will receive one of two treatment regimens according to a computer-generated randomization schedule prepared by the CCRP Pharmaceuticals, Inc. and kept at the individual investigational sites. This randomization schedule will provide for equal numbers of subjects in the two regimens. The random study group assignment will be provided for each subject in individually sealed envelopes. As a qualified subject enters the study, the next available randomization envelope in the sequence will be opened to reveal the appropriate therapy regimen. The following two regimens will be used:

- 1. Drug A 500 mg PO q12h**
- 2. Cefuroxime axetil 500 mg PO q12h**

Total therapy duration will be 7 to 14 days, as clinically indicated. A minimum of five days of therapy will be required for analysis of microbiologic response, unless subjects have failed clinically and have taken sufficient drug to be considered evaluable within this time. If, in the opinion of the investigator, a subject requires more than 14 days of therapy (e.g., *Legionella pneumophila*, slowly resolving pneumonia, etc.) the medical monitor should be contacted.

All subjects will be assessed for possible adverse events during the course of the study. All adverse events will be documented on the case record form. Safety will also be assessed by the physical examinations and laboratory tests performed pre-therapy and post-therapy.

Efficacy will be assessed by microbiological and clinical response. Microbiological data will be obtained from cultures of respiratory secretions.

Clinical response will be evaluated by assessing physical exam signs and symptoms, laboratory results, and chest X-ray findings by the investigator after the completion of therapy.

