## **E. Randomization**

As subjects qualify for the study, subject numbers will be assigned in strict sequential order at each site. Subjects will receive one of two treatment regimens according to a computer-generated randomization schedule prepared by the CCRP Pharmaceuticals, Inc. and kept at the individual investigational sites. This randomization schedule will provide for equal numbers of subjects in the two regimens. The random study group assignment will be provided for each subject in individually sealed envelopes. As a qualified subject enters the study, the next available randomization envelope in the sequence will be opened to reveal the appropriate therapy regimen. The following two regimens will be used:

- 1. Drug A 500 mg PO q12h**
- 2. Cefuroxime axetil 500 mg PO q12h**

Total therapy duration will be 7 to 14 days, as clinically indicated. A minimum of five days of therapy will be required for analysis of microbiologic response, unless subjects have failed clinically and have taken sufficient drug to be considered evaluable within this time. If, in the opinion of the investigator, a subject requires more than 14 days of therapy (e.g., *Legionella pneumophila*, slowly resolving pneumonia, etc.) the medical monitor should be contacted.

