## **VIII. STATISTICAL METHODS**

The microbiological eradication rates and clinical response rates will be compared for Drug A and Cefuroxime axetil. A Chi-square analysis will be performed to compare the rates of eradication and response between the two drugs. Using an alpha level of 0.05 and power of 85% will require a sample size of 200 subjects in each of the two groups.

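### Allocation appears to be balanced within site, yet the named test is a plain chi-square on pooled data: slightly conservative if sites differ, but not biased

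*Protocol*

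**What the plan says.** **Allocation.** Section 2.2.E (Randomization) and the Description of Study say that "subject numbers will be assigned in strict sequential order at each site". They place the schedule at the sites: "computer-generated randomization schedule prepared by the CCRP Pharmaceuticals, Inc. and kept at the individual investigational sites". On the ratio they say "This randomization schedule will provide for equal numbers of subjects in the two regimens". The next sealed envelope in sequence is opened for each qualifying subject. The Protocol Summary plans 20 to 25 sites and says "20 subjects will be enrolled from each site". Neither stratification by site nor blocking is mentioned, and the equal numbers are not tied expressly to each site.

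**Analysis.** The Description of Study says "The data will be pooled across investigators for safety and efficacy analyses". Section VIII says "A Chi-square analysis will be performed to compare the rates of eradication and response between the two drugs", followed by "Using an alpha level of 0.05 and power of 85% will require a sample size of 200 subjects in each of the two groups". No site factor is named, and no assumed rates, difference or between-site variation are given.

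**Reasons for sites to differ.** Clinical response is rated by the local investigator. Under Visit #1, cultures for the atypical organisms are done when indicated and "if the microbiology laboratory has the capability to perform these cultures".

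**The concern.** If each site has its own balanced sequence, site is a randomization stratum. Between-site differences in response then cancel from the treatment difference, but a single 2x2 table still counts them as residual variation. The estimated standard error is too large, the test rejects less often than its nominal 5%, and some power is given away. The protocol gives its own reasons to expect sites to differ, so the case is not far-fetched. What is at stake is efficiency: the validity of the comparison is not threatened.

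**Working it through.** **The protocol's own figure.** The 200 per group cannot be reproduced, because Section VIII gives no rates, difference or sidedness. As an illustration, 80% versus 90% (assumed) at alpha 0.05 and 85% power needs 228 per group two-sided, 247 two-sided with continuity correction, 182 one-sided and 202 one-sided with continuity correction. The check below therefore concerns only the relative effect of ignoring site.

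**Inputs.** From the protocol: 20 sites of 20 subjects, 200 per group, alpha 0.05 (taken as two-sided). Assumed: allocation 10:10 within each site; 85% response in both arms for type I error; 80% versus 90% for power; ICC from 0 to 0.20. The protocol gives no ICC.

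**Standard error under no effect.** The pooled chi-square uses sqrt(0.85 × 0.15 × (1/200 + 1/200)) = 0.0357. With balance within site, the true variance of the difference is about (1 − ICC) times the pooled variance:

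- ICC 0.05: 0.0357 × sqrt(0.95) = 0.0348; ratio 1/sqrt(0.95) = 1.026.
- ICC 0.10: 0.0357 × sqrt(0.90) = 0.0339; ratio 1/sqrt(0.90) = 1.054.

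**Simulation, 10:10 within site, 20,000 trials per scenario** (CMH = Cochran-Mantel-Haenszel by site):

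| ICC | Pooled SE / true SE, no effect | Type I error, pooled | Type I error, CMH | Power, pooled | Power, CMH |
|---|---|---|---|---|---|
| 0.02 | 1.003 | 4.9% | 5.1% | 80.8% | 81.0% |
| 0.05 | 1.025 | 4.7% | 5.2% | 80.3% | 81.0% |
| 0.10 | 1.051 | 4.0% | 5.0% | 80.7% | 82.3% |
| 0.20 | 1.116 | 3.0% | 5.0% | 81.3% | 84.4% |

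The estimated difference was unbiased throughout. The standard-error ratio applies under no effect. In the power scenarios treatment halves the failure rate at every site, so the absolute difference itself varies between sites and the ratio no longer exceeds 1 (0.983 at ICC 0.05, 0.965 at 0.10). CMH still has the higher power there.

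**Analytic check on power.** A design with exactly 85% power when site is ignorable has a standardized effect of 1.960 + 1.036 = 2.996. With variance reduced to (1 − ICC):

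- Pooled: Phi(1.036/sqrt(1 − ICC)) = 85.6% at ICC 0.05 and 86.3% at 0.10.
- Stratified: Phi(2.996/sqrt(1 − ICC) − 1.96) = 86.7% and 88.5%.
- Gain: 1.1 and 2.2 points.

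**With exclusions.** The protocol enrols about 450 to obtain 400 evaluable, so 50/450 = 11% may drop out. With 22 sites of 20 and 11% dropped at random, pooled type I error was 4.6% at ICC 0.05 and 4.1% at 0.10, against about 5.1% for CMH. CMH gained 0.7 and 1.8 points of power. At ICC 0 it lost about 0.4 points.

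**Eradication.** Only subjects with a baseline pathogen contribute. If 30% are evaluable (assumed; 22 sites of 20, 79% versus 90%), CMH by single site had less power than the pooled test: 36.7% versus 41.0% at ICC 0, 38.3% versus 41.3% at 0.05, and 37.6% versus 38.6% at 0.10. A second run gave losses of 1.4 to 4.7 points over the same range.

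**The case against.** **Balance within site is inferred.** This stands, and it limits confidence. Under simple 1:1 allocation the pooled test kept type I error at 4.9% to 5.0% up to ICC 0.10, so its standard error under no effect was not too large. CMH by site then had 78.5% power against 80.7% at ICC 0, and 80.5% against 79.8% at ICC 0.10. Stratifying is close to free only if allocation really is balanced within site.

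**The test may not be unstratified.** CMH is itself a chi-square test. Pooling may mean only that efficacy is judged on the combined data, since the section on maintaining records also asks each investigator for a report on his or her own part. Site adjustment may also sit in an analysis plan that is not shown. This stands in part. But the protocol does name a test and a pooling rule, and read plainly together they give one table. A stratified analysis would have to add to that text.

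**A reader might infer confounding by site** once non-evaluable subjects are dropped. The documents do not support this. With 11% dropped at random, bias was below 0.001. Confounding would need exclusions that differ by arm in a way that varies by site, and nothing in the protocol shows that. Selection of that kind is a separate problem, which stratifying by site does not generally cure.

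**A reader might set 86.7% to 88.5% against the protocol's 85%** and claim 1.7 to 3.5 points. That compares unlike things: under the same assumption the pooled test's power also rises, to 85.6% and 86.3%.

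**A reader might suppose that stratifying never costs power.** The eradication results show otherwise when strata are thin.

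**Conclusion.** The point holds as a loss of efficiency on clinical response. If allocation is balanced within site and sites differ, the pooled chi-square is conservative. At assumed ICCs of 0.05 to 0.10 its standard error under no effect is about 2.5% to 5% too large, type I error is about 4.7% to 4.0%, and about 0.7 to 2 points of power are lost. At 0.02 or below the effect is negligible. The treatment difference is not biased by pooling under balance or random exclusions. Two things rest on inference or assumption: balance within site, which is the natural reading but is unstated, and the ICC, for which the protocol gives no figure. Confidence is medium, and this is a cheap improvement rather than a correction of an invalid test.

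**What to change.** 1. In the Description of Study and Section 2.2.E, state that randomization is balanced within site. If that is not what was intended, say so, because the case for stratifying then weakens.
2. In Section VIII, replace the pooled chi-square for clinical response by a Cochran-Mantel-Haenszel test stratified by site, with a Mantel-Haenszel risk difference and 95% confidence interval. Merge small sites by a rule fixed before the data are reviewed.
3. For microbiological eradication, stratify by merged site groups, not single sites. Single-site strata would cost about 1 to 5 points of power if 30% of subjects are evaluable, which is an assumption.

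The cost is a few sentences and a few lines of code. No new data are needed.
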